2.0 SUBJECT ENTRY CRITERIA

Six subjects will participate in this study to yield six readings per test article, including both application configurations for the ChloraPrep Triple Swabsticks whereas three sites will be delineated on the abdomen, two for the ChloraPrep Triple Swabsticks and one for Hibiclen. Subjects must meet the inclusion and exclusion criteria in Sections 10.0 of the protocol to which this neutralizer validation is to be performed. The neutralization subjects do not require a minimum bacterial count, but they still need to avoid topical and systemic antimicrobials for 14 days prior to the treatment day. Each subject will receive both of the test articles, one product per side.

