4.0 TEST ORGANISM

Staphylococcus epidermidis ATCC 12228. The test organism from the frozen stock culture will be transferred into 10 mL of Tryptic Soy Broth and incubated at 30±2 C. After 24 hours of incubation this culture will be diluted into ten fold dilutions using Butterfield's Phosphate Buffered Dilution water to achieve an appropriate concentration for inoculation of the test samples.

5.0 PROCEDURE [NOTE: All testing described in this section will be performed in triplicate.]

- 5.1 Serially dilute the overnight suspension with Butterfield's phosphate buffered water (PBW) to achieve an appropriate concentration for inoculation of the test samples.

Note: The density of the test inoculum must be verified by direct plating at beginning and end of this evaluation.

5.2 **Neutralization Effectiveness Control:** Samples will be taken from the abdomen with scrub solution containing neutralizers. The subject number, location of the prep application, location of the sites sampled within the prep area, and the time of sample collection will be documented on the CRF.

5.2.1 Mark the abdominal test areas using a sterile 2" x 5" template (three sites total).

5.2.2 After the test areas are marked, prep each site with three 70% isopropyl alcohol swabs for a total of one minute and wait site to dry.

5.2.3 Prep the each site with one of the two test articles according to randomization scheme per Appendix 1 (whereas two sites will be used for ChloraPrep Triple Swabsticks, each of which will be used for one of the two application configurations).

5.2.4 Using the cup scrub technique, at 10 minute post prep collect the sample using scrub solution containing neutralizers.

5.2.5 Each pooled sample (approximately 6 mL) will be mixed on a Vortex-type mixer and immediately inoculate this tube with approximately 30-100 CFU per mL.

5.2.6 Immediately (< one minute) and at 30 minutes (\pm 2 minutes) post-inoculation, pour-plate duplicate 1.0 mL aliquots of the inoculated sample using TSA containing neutralizers. Incubate the plates at 30 \pm 2C for 72 \pm 4 hours.

5.3 **Number Controls:** Add diluted inoculum into a tube containing 6.0 mL of sampling solution without neutralizers yield final inoculum concentrations of ~30-100 CFU/mL. Plate duplicate 1.0 mL aliquots immediately (< 1 minute) and 30 minutes (\pm 2 minutes) post inoculation in the same manner as 5.2.6 above except using TSA without neutralizers.

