5.7 Data Evaluation

Recovery for each of the samples will be expressed as Log_{10} CFU/mL.

Neutralizer Effectiveness: If the Log_{10} CFU/mL of the antiseptic sample is not more than 0.3 logs less than the Numbers Control, the neutralizer will be considered effective.

Neutralizer Toxicity: If the Toxicity Control (TC) is not more than 0.3 logs less than the Numbers Control sample, the sampling solutions will be considered non-toxic.

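### The neutralizer effectiveness sample is plated only after inoculation, so any surviving skin flora count as recovered marker and can only favour a pass

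*Combined protocol and SAP*

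**What the plan says.** Appendix 2 tests whether the sampling fluid neutralizes the antiseptics, using *S. epidermidis* as the marker.

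- **Subjects (2.0).** Six subjects give six readings per article configuration. "The neutralization subjects do not require a minimum bacterial count", and no upper limit on their flora is set either.
- **Skin preparation (5.2.2 to 5.2.4).** Staff "prep each site with three 70% isopropyl alcohol swabs for a total of one minute and wait site to dry". The test article is then applied, and staff "at 10 minute post prep collect the sample using scrub solution containing neutralizers".
- **Inoculation and plating (5.2.5, 5.2.6).** The pooled sample "will be mixed on a Vortex-type mixer and immediately inoculate this tube with approximately 30-100 CFU per mL". Immediately and at 30 minutes, staff "pour-plate duplicate 1.0 mL aliquots of the inoculated sample using TSA containing neutralizers". No uninoculated portion is plated.
- **Controls (5.3, 5.4).** The Numbers Control and the Toxicity Control are made in fresh sampling solution, so neither contains anything taken from skin.
- **Evaluation (5.5 to 5.7).** Plates are counted and converted to log10. If the antiseptic sample "is not more than 0.3 logs less than the Numbers Control, the neutralizer will be considered effective". No background subtraction or identification of the marker is described.

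**The concern.** The quantity of interest is the fraction of the inoculated marker that survives in the sampling fluid. The quantity counted is that fraction plus whatever native flora came off the skin. The agar is not described as selective, and Section 9.0 of the protocol itself presents the marker species as one commonly found on skin. The comparator has no such background, and a count can fail the rule only by being too low. Any contamination by native flora therefore works in one direction.

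What is at stake is the meaning of the post-treatment counts. If the fluid does not fully stop the antiseptic, killing continues in the tube and is reported as log reduction on skin. Appendix 2 is the plan's safeguard against that. The background cannot be recovered from the planned counts once the tube has been inoculated.

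**Working it through.** The plan gives no figure for residual flora or for the bias, so there is nothing of its own to reproduce. Residual flora are treated below as an assumption and shown over a range.

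**Inputs**
- Inoculum N = 30 to 100 CFU/mL (Appendix 2, 5.2.5).
- Scrub volume 6.0 mL and cylinder area 3.8 cm² (protocol 12.4.2).
- Margin 0.3 log10 (Appendix 2, 5.7).
- For a scenario only: minimum abdominal baseline 10³ CFU/cm² and a 2.0 log10 reduction (protocol 12.2.2).

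**Step 1: pass line.** 10^(−0.3) = 0.501. The sample must reach 0.501 × 30 = 15.0 CFU/mL, or 0.501 × 100 = 50.1 CFU/mL.

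**Step 2: flora in the tube.** b = (residual CFU/cm²) × 3.8/6.0. A residual of 1 CFU/cm² gives 0.63 CFU/mL; 10 CFU/cm² (10³ reduced by 2.0 log10) gives 6.3 CFU/mL.

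**Step 3: additive model (flora counted in full).** With true marker recovery f, the expected count passes if fN + b ≥ 0.501N, so the lowest passing recovery is f = 0.501 − b/N and the tolerated loss is −log10(f).

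| Residual | N = 30 | N = 100 |
|---|---|---|
| 0 | 0.30 log | 0.30 log |
| 1 CFU/cm² | 0.501 − 0.021 = 0.480, 0.32 log | 0.501 − 0.006 = 0.495, 0.31 log |
| 10 CFU/cm² | 0.501 − 0.211 = 0.290, 0.54 log | 0.501 − 0.063 = 0.438, 0.36 log |

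**Step 4: a 60% kill (f = 0.40, loss 0.40 log), which should fail.** The flora needed to reach the pass line are (0.501 − 0.40)N = 0.101N.
- N = 30: 3.0 CFU/mL, × 6.0/3.8 = 4.8 CFU/cm².
- N = 100: 10.1 CFU/mL, × 6.0/3.8 = 16.0 CFU/cm².
- With 6.3 CFU/mL of flora, the expected count passes only for N up to 6.33/0.1012, about 63 CFU/mL.

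**Step 5: equal-kill model.** The flora sit in the same tube as the carried-over antiseptic. If they also lose 60%, the condition is 0.40(N + b) ≥ 0.501N, so b ≥ 0.253N.
- Required flora: 7.6 CFU/mL at N = 30 and 25.3 CFU/mL at N = 100, about 12 to 40 CFU/cm².
- At 10 CFU/cm², expected recovery is 0.40 × (30 + 6.3) = 14.5 against 15.0, and 0.40 × (100 + 6.3) = 42.5 against 50.1. Both still fail.

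**Step 6: counting error.** These are simulated probabilities that one sample passes at f = 0.40 in the additive model, with Poisson counts on duplicate 1.0 mL plates for both the sample and the Numbers Control.

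| Residual 10 CFU/cm² | N = 30 | N = 100 |
|---|---|---|
| No flora (reference) | 0.16 | 0.04 |
| Flora counted, as planned | 0.81 | 0.26 |
| One 1.0 mL blank plate subtracted | 0.24 | 0.06 |

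Subtracting a blank brings the pass probability close to the value without flora. What remains is counting error from the single blank plate.

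**The case against.** The strongest reply is that little flora should be left. Every site gets a one-minute alcohol prep before the antiseptic, and the antiseptic then acts for 10 minutes. With no minimum count required, these subjects may also start below 10³ CFU/cm². The 10 CFU/cm² scenario applies the main study's 2.0 log10 criterion to its minimum baseline and gives no weight to the alcohol step. Nothing in the documents places the residual at 10 rather than 1, where the effect is negligible. This stands, and it limits the size. It does not remove the gap, because the residual is neither measured nor capped.

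A reader might infer that a residual of 10 CFU/cm², the level left by a just-passing abdominal site, is enough to overturn the verdict. The documents do not support this. It holds for a 60% kill only at inocula up to about 63 CFU/mL, and only if the antiseptic spares the flora while killing the marker. A 60% kill is also a borderline failure, 0.10 log beyond the tolerated loss. Complete loss of marker would need flora of at least 15.0 × 6.0/3.8 = 23.7 CFU/cm² at N = 30, or 79.1 CFU/cm² at N = 100, untouched by an antiseptic that destroyed all the marker. Hiding a partial failure is the more plausible case.

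Three smaller points also stand:
- There are six readings per article configuration, a triplicate note and two plating times, so masking across the panel needs residual flora at many sites.
- The documents do not say whether marker and native colonies could be distinguished by eye; they only describe no attempt to do so.
- Undetected carry-over would inflate reductions for both chlorhexidine products relative to water, but the direction of bias between ChloraPrep and Hibiclens is not fixed.

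**Conclusion.** The concern holds as a missing control of unknown consequence. As written, the effectiveness sample mixes marker and native flora, the comparator has no flora, and the rule cannot fail on excess counts, so the bias can only favour a pass.

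Its size depends on a residual that the plan does not measure: negligible near 1 CFU/cm², and material near 10 CFU/cm² mainly at the low end of the inoculum range. The additive figures are an upper bound. Under equal kill, hiding a 60% loss needs about 12 to 40 CFU/cm². It would go too far to conclude that the validation will hide a neutralizer failure or that the trial's counts are invalid; the documents support only that such masking could not be detected. This is an inexpensive improvement, not a fundamental defect.

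**What to change.** **Appendix 2, 5.2.5.** After vortexing and before inoculation, pour-plate one 1.0 mL aliquot of each pooled sample in the same neutralizing agar, incubated as in 5.2.6. Set the inoculum on the remaining volume, about 5 mL.

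**Appendix 2, 5.7.** Subtract the blank count (CFU/mL) from the inoculated counts before applying the 0.3 log rule. Alternatively, require the blank to be below a small pre-set fraction of the inoculum for the reading to be valid.

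**Cost.** Volume suffices: 1 mL for the blank plus 2 × 2 mL for duplicate plates at two times is 5 of about 6 mL, although the aspirated volume may run a little short. Six subjects × three sites is 18 extra plates, more if the triplicate note in 5.0 applies to each sample. No subject, visit or skin procedure is added. Inoculation is briefly delayed; keep the delay short and uniform, since it gives the neutralizer extra time before the marker arrives. A single blank plate adds a little counting error, and a time-zero blank may over-subtract at 30 minutes, which errs on the strict side. The change has to be made before the validation is run.

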5.5 Enumerate plates and calculate CFU/mL for each sample

5.6 Convert data to Log_{10} CFU/mL.

5.7 Data Evaluation

Recovery for each of the samples will be expressed as Log_{10} CFU/mL.

Neutralizer Effectiveness: If the Log_{10} CFU/mL of the antiseptic sample is not more than 0.3 logs less than the Numbers Control, the neutralizer will be considered effective.

Neutralizer Toxicity: If the Toxicity Control (TC) is not more than 0.3 logs less than the Numbers Control sample, the sampling solutions will be considered non-toxic.
